9.4 Safety Analysis

Safety is the primary objective of this study. The overall safety profile of VX-121 will be assessed in terms of the following primary (safety) endpoints:

- Incidence of treatment-emergent adverse events (TEAEs)
- Clinical laboratory values as specified in the CSP.
- ECG outcomes
- Vital signs (including pulse oximetry [Part D only])
- Spirometry (Part D only)

All safety analyses will be performed by treatment group/treatment sequence for each part as applicable based on the Safety Set. All safety data will be presented in the individual subject data

listings based on the All Subjects Set. No statistical hypothesis testing will be performed for safety analysis.

Table 9-1 shows the safety summaries (e.g., raw value, change from baseline, incidence, and clinical abnormalities and etc) that will be summarized for TEAEs, clinical lab values, 12-lead ECGs, vital signs, spirometry and physical examination. Details are provided in the corresponding subsections.

The incidence of TEAEs will be summarized. TEAE summaries will include the following: all TEAEs (regardless of severity or relationship to study drug), serious adverse events (SAEs), TEAE severity, TEAE relationship, and discontinuations of study drug treatment due to TEAEs.

For the non-AE safety evaluations (clinical laboratory, ECGs and vital signs), raw values, and changes from baseline will be summarized as indicated in **Table 9-1**. For example, an “X” under the raw value column (third column) means that the “Raw value” for the safety evaluation will be summarized in tables; an “X” under the “Change from Baseline” column (fourth column) means that change will be summarized in tables.

Throughout this section, “change” refers to absolute change from baseline.

Table 9-1 Summaries Planned for Safety Data

Safety Assessment	Incidence	Raw Value	Change from Baseline	Clinical Abnormalities	Threshold Analysis
TEAEs	X			NA	
Hematology/and chemistry		X	X	Listing only	X (Part D only)
Coagulation		X (Part D only)	X (Part D only)		
Urinalysis		Listing only			
12-lead ECG		X	X		X (Part D only)
Vital signs		X	X		X (Part D only)
Spirometry (Part D)		X	X	NA	
Physical Examination		Listing only		NA	

ECG: electrocardiogram; TEAEs: treatment-emergent adverse events; NA: Not applicable; X: safety assessment will be summarized in tables

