i Standard 12-lead ECGs will be performed in the supine position after the subject has been at rest for at least 5 minutes. The ECG will be done before any other procedures that may affect heart rate, such as blood draws. On Days 1 and 15, ECGs will be collected before dosing and 4 hours (± 1 hour) after dosing. ECGs collected on Day 1 before dosing will be performed in triplicate.

j The predose assessment on Day 1 may be performed on the previous day (Day -1) if randomization has occurred.

k Sweat chloride will be measured in all subjects. See [Section 8.2.1](#) for information about the sweat chloride assessment for study eligibility.

l Spirometry may be performed pre- or post-bronchodilator at the Screening Visit. Spirometry will be performed pre-bronchodilator, before the morning dose of study drugs, and should be performed at approximately the same time at every other study visit. On Days 1 and 15, spirometry will also be performed pre-bronchodilator 5 hours (± 1 hour) after study drug administration.

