## Spirometry

Mild post-dose declines in lung function have been observed after the initial dose with another CFTR corrector not included in the current study (LUM). Although nonclinical toxicity results do not indicate a risk of lung function declines for VX-121, lung function, as assessed by spirometry, will be included in Part D to assess for post-dose declines in spirometric indices. In addition, lung function, as assessed by spirometry, will be evaluated for preliminary evidence of efficacy.

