#### **12.3.4 Safety Analysis**

Safety is the primary objective of this study. The overall safety profile of VX-121 will be assessed in terms of the following primary (safety) endpoints:

- Incidence of treatment-emergent adverse events (TEAEs)
- Clinical laboratory values (including coagulation studies)
- ECG outcomes

- Vital signs
- Spirometry (Part D only)

Safety analyses will be based on the Safety Set. No statistical hypothesis testing will be conducted.

For safety variables, the baseline value will be defined as the most recent non-missing measurement collected before the initial administration of study drug.

All safety data will be presented in individual subject data listings.

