- **TE Period 2 (tablet [fed])** will begin from administration of VX-121 tablet in the fed state (1) until the administration of VX-121 tablet in the fed state and with milk, or (2) the Safety Follow-up Visit for subjects who do not have the dose of VX-121 tablet in the fed state and with milk and have a Safety Follow-up Visit, or (3) 7 days after the last dose of study drug for subjects who do not have the dose of VX-121 tablet in the fed state and with milk, and do not have a Safety Follow-up Visit.
- **TE Period 3 (tablet [fed and with milk])** will begin from the administration of VX-121 tablet in fed state and with milk through the Safety Follow-up Visit or 7 days after the last dose of study drug for subjects who do not have a Safety Follow-up Visit..

For subjects participating in Part D, the **TE Period** will be from first dose date of study drug to Safety Follow-up Visit for subjects who have a safety follow-up visit; or 28 days after the last dose date of study drug for subjects who do not have a safety follow-up visit.

Treatment Groups

The Treatment Groups in Part A (excluding Cohorts A3 and A9), B, C and D will be defined as the corresponding VX-121 dose groups.

The 2 Treatment Groups in Cohort A3 will correspond to suspension [fed] and suspension [fed and with milk] respectively.

The 3 Treatment Groups in Cohort A9 will correspond to suspension [fed], tablet [fed] and tablet [fed and with milk] respectively.

Baseline value

The baseline value will be defined as the most recent non-missing measurement (scheduled or unscheduled) collected before the first dose of study drug. If a pre-dose measurement is missing and no drug-free unscheduled assessments are performed before the first dose of the study, the baseline will be missing. For ECG, the baseline value will be defined as the most recent non-missing measurement (or the average of triplicate measurements, if the most recent non-missing measurements are obtained in triplicate), before the first dose of study drug of the Treatment Period.

Absolute change from baseline will be calculated as post-baseline value – baseline value.

Relative change from baseline will be calculated as (post-baseline value – baseline value)/baseline value.

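### The SAP plans no same-day postdose-minus-predose change for Part D spirometry, so at Day 15 an acute fall is mixed with any gain since baseline

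*SAP*

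**What the plan says.** **Purpose.** Protocol 9.3.3 (Spirometry) states that "lung function, as assessed by spirometry, will be included in Part D to assess for post-dose declines in spirometric indices". The background it gives is that "Mild post-dose declines in lung function have been observed after the initial dose with another CFTR corrector", one that is not used in this study. The same paragraph adds preliminary evidence of efficacy as a second use. Spirometry in Part D is part of the primary safety endpoint (Protocol 7.1, SAP 6.1).

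**Data.** Every treatment visit has a predose test. Protocol Table 3-7, footnote l, adds: "On Days 1 and 15, spirometry will also be performed pre-bronchodilator 5 hours (± 1 hour) after study drug administration".

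**Baseline.** SAP 9.1: "The baseline value will be defined as the most recent non-missing measurement (scheduled or unscheduled) collected before the first dose of study drug". Protocol 12.3.4 has the same rule for safety variables: "the baseline value will be defined as the most recent non-missing measurement collected before the initial administration of study drug".

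**Safety analysis.** In SAP 9.4, change "refers to absolute change from baseline" throughout the section. Table 9-1 plans raw value and change from baseline for spirometry. Clinical abnormalities are marked not applicable, and the threshold column is empty. The visible subsections of 9.4 include none for spirometry. All safety data are to be listed by subject.

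**Analysis visits.** SAP Table 12-1 gives the ECG a Day 1 postdose visit and predose and postdose visits at Day 15. Spirometry has Baseline, Day 8 with window (1, 12], Day 15 with window (12, 22], Day 29 and Safety Follow-up. It has no Day 1 postdose visit and no split at Day 15. If two values in a window are equally far from the target day, the later one is used.

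**The concern.** A postdose test is informative about an acute effect when it is compared with the test taken a few hours before on the same day. The visible text of the protocol and SAP defines no such comparison. The only planned change takes the value before the first dose as its reference. At Day 15 that value is about two weeks old, and the active arm may have improved in the meantime.

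Part D also looks for efficacy, so a gain by Day 15 is the hoped-for result. The planned change is therefore least able to show an acute fall at Day 15 if the treatment works. A fall smaller than the gain would appear in the safety table as an improvement.

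**Working it through.** The plan states no effect size, SD or threshold for postdose spirometry, so there is no figure of its own to reproduce. The point rests on an identity and on the visit-window rules.

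**1. Identity.** Let B be the baseline value, P the Day 15 predose value and Q the Day 15 postdose value.

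Q − B = (P − B) + (Q − P)

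That is, reported change = gain since baseline + same-day change. With G = P − B and an acute fall D = P − Q, the reported change is G − D and the same-day change is −D.

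**2. Illustration.** All values are assumed, in ppFEV1 points, with an acute fall D = 5.

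| Gain G | Change from baseline, G − D | Same-day change, −D |
|---|---|---|
| 0 | −5 | −5 |
| 2 | −3 | −5 |
| 5 | 0 | −5 |
| 10 | +5 | −5 |

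**3. Individual subjects.** Assume a same-day change with mean −5 and SD 3, and an independent gain with SD 3 to 6, all normal. About 50% of subjects then have a same-day fall of 5 points or more. The share with a change from baseline of −5 or lower is Φ[(−5 − (mean gain − 5)) / √(SD of gain² + 3²)].

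| Mean gain | Gain SD 3 | Gain SD 6 |
|---|---|---|
| 0 | 50% | 50% |
| 5 | Φ(−5/4.24) = 12% | Φ(−5/6.71) = 23% |
| 10 | Φ(−10/4.24) = 1% | Φ(−10/6.71) = 7% |

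A simulation with the same inputs gave the same shares.

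**4. Day 1.** Baseline is normally the Day 1 predose test, so P = B and G = 0. The Day 1 postdose change from baseline is then already the same-day change.

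**5. Can the Day 15 fall be recovered from the planned tables?** If predose and postdose means were tabulated separately for the same subjects, mean(Q) − mean(P) = mean(Q − P), which gives the mean fall. It does not give the SD of Q − P or the number of subjects who fell.

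Table 12-1 does not assure even the two means. For a visit on Day 14, 15 or 16, the predose and postdose tests fall on the same study day. They are equally far from Day 15, so the tie rule keeps the later one, the postdose value. The Day 1 postdose test is on study day 1, which lies outside (1, 12]. The footnote that lets Day 1 postdose values into the Day 8 window is attached to the laboratory and vital-sign rows, not to spirometry.

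**The case against.** The strongest reply has four parts.

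- **The cited risk is the initial dose.** This stands. The precedent in Protocol 9.3.3 concerns the first dose, and Day 1 is not masked. A reader might infer that a steady-state acute fall is the declared reason for the Day 15 postdose test. The documents do not say so: they give a general aim of assessing postdose declines, and Table 3-7 schedules Day 15 without giving a reason. Even so, the test is repeated at Day 15, and the general aim covers it.

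- **Raw values and listings are planned.** This stands in part. A reader might infer that the Day 15 fall cannot be obtained from the output. That is too strong. Part D has about 12 subjects (9 active, 3 placebo in Protocol Figure 9-1), and the listings allow subtraction subject by subject. Separate means would give the average fall, but step 5 shows that they are not assured. SAP 9.3.1 does specify predose values for the mixed model, but those are model-based estimates on the Full Analysis Set, with no postdose counterpart.

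- **Safety is descriptive, with no testing and no sample-size calculation.** True, but the missing summary would be descriptive too.

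- **A same-day contrast cannot take the place of change from baseline.** This stands. A sustained fall from baseline with no acute part would then drop out of the Safety Set summary. Change from baseline is also the change that the protocol's baseline rule for safety variables supports. The contrast must be added to it.

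**Conclusion.** The point holds for Day 15. The planned change from baseline mixes any gain since baseline with the acute effect of the dose, and no same-day contrast is defined in the visible text. The fall is understated whenever predose lung function has improved, and its sign is reversed when the gain exceeds the fall. This follows from the identity alone. The size is unknown, because the documents give no effect sizes or SDs, and the numbers above are illustrations.

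It would go too far to say that the plan conceals a safety signal. Day 1 is free of this masking provided baseline is that day's predose test, and individual values at both days will be listed. What is missing is a planned summary that answers the stated question at Day 15, together with time points that would let the tables show it. The gap is modest and cheap to close, and should be closed before database lock.

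**What to change.** 1. **SAP Table 12-1:** for spirometry, define Day 1 postdose, Day 15 predose and Day 15 postdose as separate analysis time points, as is done for the ECG. This also keeps the tie rule from selecting the postdose value where SAP 9.3.1 calls for the predose one.

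2. **SAP 9.4:** add a short spirometry subsection. For FEV1 and ppFEV1, summarise the same-day change (5-hour postdose minus that day's predose) on Days 1 and 15, by treatment group on the Safety Set, and list the individual values. Show placebo alongside to allow for change over the day; with about 3 placebo subjects this is only a rough guide.

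3. **Keep** the change-from-baseline safety summary.

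Cost: one SAP paragraph, small edits to Table 12-1 and one table. No new data or procedures are needed.

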9.4.1 Adverse Events

AEs will be coded according to MedDRA (Version 20.1 or above). The number and percentage of subjects experiencing an AE will be summarized by the MedDRA System Organ Class (SOC) and Preferred Term (PT). AEs will be classified as pretreatment or treatment-emergent.

Pretreatment AEs are defined as AEs that were reported or worsened (either in severity or seriousness) after signing the ICF up to the start of study drug dosing.

Treatment-emergent adverse events (TEAEs) for all cohorts except Cohorts A3 and A9 are defined as any AE that worsened (either in severity or seriousness) or that was newly developed at or after the first dose date of study drug during the Treatment Period through the end of the TE Period for the Treatment Period.

For Cohort A3 and A9, TEAEs will be assigned to each treatment group based on the start date of the AE and the start of study drug administration dates within the corresponding TE Period.

For AEs with completely missing or partially missing start dates, if there is no clear evidence that the AEs started before or after study treatment, the AEs will be classified as TEAEs corresponding to the Treatment Period. Unless otherwise specified, TEAE refers to TEAE during the Treatment Period.

Details for imputing missing or partial start dates of adverse events are described in [Appendix C](#), which is applicable to Part D only.

AE summary tables will be presented for TEAEs only and will include the following: (1) Overview of TEAEs (2) all TEAE; (3) related (defined as possibly related, related, or missing) TEAEs; (4) serious TEAEs; (5) TEAEs by severity; (6) TEAEs by relationship; and (7) TEAEs leading to treatment discontinuation.

Summaries will be presented using frequency counts and percentages by treatment group/treatment sequence for each part (i.e., number and percentage of subjects with an event); for the summary table of TEAE Overview, an additional column of overall will be provided.

When summarizing the number and percentages of subjects, subjects with multiple occurrences of the same adverse event will be counted once, and only the maximum severity level will be presented in the severity summaries, and the strongest relationship level in the relationship summaries.

In addition, a listing containing individual subject AEs leading to death, SAEs, dose interruption, and discontinuation will be listed separately. All AEs through the Safety Follow-up Visit will be listed in an individual subject data listing, including pretreatment AEs.

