#### **12.3.4.1 Adverse Events**

AEs will be coded according to MedDRA. The number and percentage of subjects experiencing an AE will be summarized by the MedDRA System Organ Class (SOC) and Preferred Term (PT). AEs will be classified as pretreatment or treatment-emergent.

**Pretreatment AEs** are defined as AEs that were reported or worsened after signing the ICF up to the start of study drug dosing.

**TEAEs during the Treatment Period** are defined as any AE that worsened (either in severity or seriousness) or that was newly developed at or after the first dose date of study drug through the end of the TE Period for the Treatment Period.

Only TEAEs will be summarized in tables. All summaries of TEAEs will be presented by the severity of the AE and relationship to the study drug. Some rules that will apply to the summarization of AEs are (1) a subject with multiple occurrences of the same AE or a continuing AE will be counted only once; (2) only the maximum severity level will be presented in the severity summary; and (3) only the worst relationship level will be presented in the relationship summary.

AEs leading to death, other SAEs, dose interruption, and permanent discontinuation will be listed separately. All AEs through the Safety Follow-up Visit will be listed in an individual subject data listing, including pretreatment AEs.

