### **13.1.1.3 Documentation of Adverse Events**

All AEs will be collected from the time ICF is signed until the following time points:

- For subjects who do not enroll: until time of screen failure (e.g., screen failure, withdrawal of consent)
- For enrolled subjects who have a Safety Follow-up Visit: through the Safety Follow-up Visit
- For enrolled subjects in Parts A, B, and C who do not have a Safety Follow-up Visit, 10 days after the last dose of study drug
- For enrolled subjects in Part D who do not have a Safety Follow-up Visit, the earliest of
  - 28 days after the last dose of study drug, or
  - the ETT Visit, if that visit is 3 weeks or later following the last dose of study drug (see [Section 9.1.2.4](#))

All subjects will be queried, using nonleading questions, about the occurrence of AEs at each study visit. When possible, a constellation of signs and/or symptoms will be identified as 1 overall event or diagnosis. All AEs for enrolled subjects will be recorded in the CRF and source document. AEs for subjects who are screened but not subsequently enrolled in the study will be recorded only in the subject's source documents. The following data will be documented for each AE:

- Description of the event
- Classification of “serious” or “nonserious”
- Date of first occurrence and date of resolution (if applicable)
- Severity
- Causal relationship to study drug(s)
- Action taken
- Outcome
- Concomitant medication or other treatment given

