9 STATISTICAL ANALYSIS

9.1 General Considerations

The Schedule of Assessments is provided in Section 3 of CSP. The precision standards for reporting safety and efficacy variables are provided in an internal Biometrics document that specifies the programming rules including the precision for derived variables.

Continuous data will be summarized using the following descriptive summary statistics: the number of subjects (n), mean, standard deviation (SD), median, minimum value (min), and maximum value (max).

Categorical data will be summarized using frequency counts and percentages. Percentages will be presented to 1 decimal place, unless otherwise specified.

Treatment-emergent (TE) Period

For subjects participating in Part A (excluding Cohorts A3 and A9), Parts B and C, the **TE Period** will be from the first dose date of study drug to (1) the Safety Follow-up Visit for subjects who have a Safety Follow-up Visit, or (2) 7 days after the last dose of study drug for subjects who do not have a Safety Follow-up Visit.

For subjects participating in Cohort A3 in Part A, 2 TE periods will be analyzed:

- **TE Period 1 (suspension [fed])** will begin from the administration of study drug on Day 1 (1) until the administration of VX-121 in fed state and with milk, or (2) the Safety Follow-up Visit for subjects who do not have the dose of VX-121 in fed state and with milk, and have a Safety Follow-up Visit, or (3) 7 days after the last dose of study drug for subjects who do not have the dose of VX-121 in fed state and with milk, and do not have a Safety Follow-up Visit.
- **TE Period 2 (suspension [fed and with milk])** will begin from the administration of study drug on Day 9 through the Safety Follow-up Visit or 7 days after the last dose of study drug, whichever comes first.

For subjects participating in Cohort A9 in Part A, 3 TE periods will be analyzed:

- **TE Period 1 (suspension [fed])** will begin from the administration of study drug on Day 1 (1) until the administration of VX-121 tablet in the fed state, or (2) the Safety Follow-up Visit for subjects who do not have the dose of VX-121 tablet in the fed state and have a Safety Follow-up Visit, or (3) 7 days after the last dose of study drug for subjects who do not have the dose of VX-121 tablet in the fed state and do not have a Safety Follow-up Visit.

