9.2.4 Prior and Concomitant Medications

Medications will be coded using the World Health Organization-Drug Dictionary (WHO-DD) September 2017, Format B2 or higher. Medications used in the study will be categorized as prior and/or concomitant medications as follows:

1. **Prior medication:** Medication that started before the first dose of study drug, regardless of when dosing of the medication ended
2. **Concomitant medication:** Medication received at or after the first dose of study drug, medication that was received before initial dosing and continued after initial dosing of study drug, or medication with missing stop date

If a medication start date is on or after the date of initial dosing of the study drug, then the medication will be summarized as concomitant medication regardless of whether the medication end date is missing or not. If a medication end date is before the date of initial dosing of the study drug, then the medication will be summarized as prior medication regardless of whether the medication start date is missing or not. Note that medication that started before initial dosing of the study drug and continued after initial dosing will be summarized as prior medication and separately as concomitant medication.

Missing or partial dates will be imputed for medication. Algorithm for missing or partial start date is:

- Missing day: first day of the month is imputed;
- Missing month: January is imputed;
- Missing year: not imputed.

Algorithm for missing or partial end date is:

- Missing day: last day of the month is imputed;
- Missing month: December is imputed (31 December if day is also missing);
- Missing year: not imputed.

Missing data algorithms will be reviewed to ensure the algorithms work. For example, end date will not be before the start date after the imputation.

For Cohorts A3 and A9, concomitant medications will be assigned to each TE period based on the start date of the medication and the study drug administration dates (concomitant medications taken during the TE period will be assigned to the TE period, and so forth).

Note that a concomitant medication may be assigned to multiple TE periods.

Prior medications will not be summarized, but will only be listed based on All Subjects Set. Concomitant medications will be summarized using preferred name by treatment group/treatment sequence and overall for each part. Concomitant Medications summary will be based on the Safety Set.

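### In Cohorts A3 and A9 the SAP places TEAEs by AE start date and omits worsening, so a worsening after a later VX-121 dose can be missing from that treatment's column

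*SAP*

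**What the plan says.** Protocol 12.3.4.1 defines a TEAE as "any AE that worsened (either in severity or seriousness) or that was newly developed at or after the first dose date". The window runs to the end of the treatment-emergent (TE) period. It exempts no cohort.

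SAP 9.4.1 narrows the reach of that definition: "Treatment-emergent adverse events (TEAEs) for all cohorts except Cohorts A3 and A9 are defined as any AE that worsened (either in severity or seriousness"). The same sentence also covers new onset. For the two excluded cohorts the section has one sentence: "For Cohort A3 and A9, TEAEs will be assigned to each treatment group based on the start date of the AE". The start date is compared with the dosing dates of each TE period. Worsening is not mentioned there.

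These are the cohorts in which the same person changes treatment. SAP 9.1 gives A3 two TE periods and A9 three, each closed by the next dose. A3 Period 1, for example, "will begin from the administration of study drug on Day 1 (1) until the administration of VX-121 in fed state and with milk". Under protocol 9.1.1 (Table 9-1, note a) all A3 subjects, including those randomized to placebo, take open-label VX-121 with milk as their second dose.

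Two counting and recording rules also bear on the point. SAP 9.4.1 shows only the maximum severity and the strongest relationship per subject and event. Protocol 13.1.1.3 has the site document "Date of first occurrence and date of resolution (if applicable") for each event, and no date of worsening is on its list.

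**The concern.** The documents treat worsening as a route to TEAE status that is separate from new onset. An onset date cannot show when an event worsened. In a cohort with one TE period that matters only for events present at baseline. In A3 and A9 it also decides which treatment an event is reported under.

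Suppose an event is mild after the first dose and becomes severe after the second. By onset date it belongs to the first period. If it is a single record, the severe grade, and any later judgement that it is drug-related, are tabulated there, while the column for the dose that preceded the worsening shows nothing. TEAE incidence is a primary safety endpoint (SAP 9.4), so a signal on the later treatment could be lost from the tables.

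**Working it through.** The plan states no figure on this point, so there is nothing to reproduce. The check applies the SAP rule to the planned dosing days.

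**Inputs**
- Dosing days: A3, Days 1 and 9 (protocol Table 3-3 notes); A9, Days 1, 9 and 17 (protocol Table 3-4 notes).
- Cohort sizes: about 8 each. A3 is randomized 3:1, so 8 × 3/4 = 6 on VX-121 and 8 × 1/4 = 2 on placebo in Period 1. All 8 in A9 receive VX-121 throughout.
- Rule: assignment is "based on the start date of the AE and the start of study drug administration dates within the corresponding TE Period". The dosing dates only mark where the periods begin and end, so the event's start date alone decides.

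**Step 1: where hypothetical events fall.** Period by start date = number of dosing days on or before the start day.

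| Cohort | Starts | Worsens | Period by start date | Period of worsening |
|---|---|---|---|---|
| A3 | Day -1 | Day 2 | none | 1 |
| A3 | Day 5 | Day 10 | 1 | 2 |
| A9 | Day -1 | Day 2 | none | 1 |
| A9 | Day 5 | Day 10 | 1 | 2 |
| A9 | Day 12 | Day 18 | 2 | 3 |

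In every row the two periods differ. In the Day -1 rows the event falls in no TE period, and only TEAEs are tabulated.

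**Step 2: effect of one event on the tables.** Take an A3 subject with a mild event on Day 5 after placebo that becomes severe on Day 10 after VX-121 with milk. Assume one record and no other event of that type in the cohort.

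| Column | SAP as written | Worsening counted in its own period |
|---|---|---|
| Placebo | 1/2 = 50%, severe | 1/2 = 50%, mild |
| VX-121 with milk, placebo sequence | 0/2 = 0% | 1/2 = 50%, severe |
| VX-121 with milk, both sequences | 0/8 = 0% | 1/8 = 12.5%, severe |

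Placebo incidence changes by 50% − 50% = 0 points; only its severity label changes. The later column is understated by 50 points within that sequence, or by 12.5 points across both. In A9 the later period likewise goes from 0/8 to 1/8, a gain of 12.5 points, and the earlier period's incidence does not move.

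**Step 3: how many treatment changes are exposed.** A3: 8 × 1 = 8. A9: 8 × 2 = 16. Total: 8 + 16 = 24. Of these, 2 are placebo to VX-121. The other 24 − 2 = 22 are VX-121 to VX-121 at the same planned dose, differing in formulation or milk. These are opportunities for the problem, not expected events.

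**The case against.** The strongest objection is that the site may enter a worsening as a new event. Protocol 13.1.1.1 counts worsening of a pre-existing condition after consent as an AE in itself. If it is recorded separately, its date of first occurrence is the date of worsening and the start-date rule places it correctly. Protocol 11.7.1 leaves recording to separate CRF completion guidelines, which are not in these documents. SAP Appendix C (Part D only) also classifies events with imputed dates by comparing the start date with the TE period, even though Part D's definition includes worsening. This stands as a condition on the finding. It does not remove it: the protocol and SAP do not require a new record, protocol 13.1.1.3 asks for a single onset date, and protocol 12.3.4.1 speaks of a continuing AE that is counted once.

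A second objection is that the A3/A9 sentence only allocates events already classed as TEAEs, so the protocol can still supply the definition. That is a fair reading. A reader might infer that the SAP deliberately removes worsened events in these cohorts from the TEAEs, but the text does not establish that intent. Even on the milder reading, a pre-Day 1 event that worsens has no period to go to, and a later worsening still follows its onset date.

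A third objection is that little depends on these columns. There is no hypothesis testing of safety data, every AE is listed individually, and dose escalation (protocol 9.7.1) and halting (protocol 9.8.1) rest on ongoing review and on events, not on period tables. This is right and limits the importance. The listings are only a partial remedy, because no worsening date is among the data to be documented.

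**Conclusion.** The point holds as a gap in a stated rule. SAP 9.4.1 drops worsening for A3 and A9, protocol 12.3.4.1 does not, and the SAP gives no rule for an event that spans two periods. If a worsened AE remains one record, the later treatment loses the event and the earlier one carries its worst grade and strongest relationship. Per event, the later column is short by 1/2 in the A3 placebo sequence (1/8 across both sequences) or by 1/8 in an A9 period. The number of such events is not given and is probably small.

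Two stronger conclusions are not supported. A reader might infer that the rule inflates placebo or earlier-formulation incidence, by 50 points for one event in a 2-subject column. It does not: an event that truly began in that period is a TEAE there under either rule. A reader might also take all 24 treatment changes as shifts from placebo to active drug, but only about 2 are.

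The correction is worth making because it is cheap and concerns a primary safety endpoint. It does not threaten the study's conclusions.

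**What to change.** In SAP 9.4.1, apply the protocol definition to A3 and A9 by period:
- An AE is a TEAE of each TE period in which it newly developed or worsened in severity or seriousness. This includes an AE that began before Day 1 and worsened after dosing.
- The severity and relationship shown for a period are the worst within that period.
- A continuing AE is counted once per period and once in any overall column. This reconciles the change with the count-once rule in protocol 12.3.4.1.
- A worsening is identified by its own AE record or by a recorded worsening date, and the CRF completion guidelines should say which.

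The cost is one or two sentences and a small programming change, plus a check that the worsening date can be obtained from the data collected. The downside is that one event may appear in two period columns. The SAP already accepts this for medications in these cohorts (SAP 9.2.4): "Note that a concomitant medication may be assigned to multiple TE periods". If sites already enter each worsening as a new record, the change alters nothing.
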